The battle of Mosul was characterized by the use of improvised explosive devices, human shields and suicide bombers in an urban setting. It is unclear whether this type of warfare cause more extensive abdominal injuries to civilians than combatants. Understanding of the correlation between the severity of abdominal injuries, type of warfare and population affected is of importance when planning for surgical care in a conflict setting.

Aim

To assess whether civilians obtain more extensive abdominal injuries than combatants in an urban battle characterized by the use of indiscriminate weapons.

Study Design

An observational retrospective cohort study with longitudinal data collection.

All patients admitted with penetrating abdominal injury subjected to an exploratory laparotomy at Emergency Hospital, Erbil, between October 17, 2016 and July 16, 2017 will be included. Differences in demographics, injury mechanism, time since injury, clinical status on arrival, intraoperative findings, postoperative complications and outcome will be analysed.

Primary Objective

Differences in injury mechanism, organs injured, surgical treatment given, postoperative complications and outcome between civilians *and* combatants.

Secondary Objectives

Differences in surgical treatment given, postoperative complications and outcome between patients with prior surgical treatment of their injury *and* patients without prior surgical treatment.

Differences in surgical treatment given, postoperative complications and outcome between patients who receive surgical treatment less than 24 hours from injury *and* patients who receive surgical treatment more than 24 hours from injury will be analysed.

Statistical methods

Differences between groups will be analysed using t-test and regression models.

List of Abbreviations

EH	Emergency Hospital, Erbil, Iraq
Ex-lap	Exploratory laparotomy
ICRC	International Committee of the Red Cross
IED	Improvised Explosive Device
ISg	Islamic State Group
WHO	World Health Organization

List of Definitions

Civilians	Children <16 years, all women and men \geq 50 years.
Combatants	Men 16-50 or combatants by own admission.
Exploratory laparotomy	Surgical incision through the abdominal wall into the abdominal cavity
PATI	Penetrating Abdominal Trauma Index Assess the severity of injury in patients with knife, gunshot or other penetrating wounds to the abdomen (appendix 1).
Penetrating abdominal injury	An injury penetrating the peritoneum into the abdominal cavity
Peritonitis	Rigid involuntary general tenderness of the abdominal wall.
Postoperative complication	Any deviation from the ideal postoperative course that is not inherent in the procedure and does not comprise a failure to cure. Classification of Surgical complications will be done according to Clavien-Dindo (appendix 2).
SSI	Surgical Site Infection is present when one of the following criteria are met: i. Purulent discharge from surgical site ii. Positive culture iii. Surgical site requires reopening iv. SSI is present as judged by attending physician Severity according WHO guidelines (appendix 3).

Background

Trail location

In 2014, Islamic State Group (ISg) made significant territorial gains in several governorates in Iraq and captured key cities, including Fallujah and Mosul¹. ISg is unique among terrorist groups in that it employs a combination of conventional maneuverer warfare with tactics such as human shields, improvised explosive devices (IED's), suicide bombers and drones in order to capture and hold territory. These tactics are indiscriminate, leading to excessive civilian casualties².

Emergency Hospital (EH) is one of two trauma hospitals in Erbil, a major metropolitan area in Kurdistan Region of Iraq. Erbil is located 94 kilometres east of the city of Mosul. Mosul is the provisional capital of the Nineveh region of Iraq. In mid-October 2016, the offensive to liberate Mosul from the ISg was initiated. EH was assigned by the Governate to exclusively provide care to injured from the armed conflict in and around Mosul. Since late December 2016 treatment facilities, run by other emergency care providers, have opened closer to Mosul. EH since then mainly served as a referral hospital.

The battle of Mosul formally ended on 10 July, 2017. The admission of casualties from Mosul to EH has since then diminished significantly. NGOs and other emergency care providers have also decreased their activities since.

Previous reports on exploratory laparotomy in conflict settings

Outcome of exploratory laparotomy (ex-lap) following war-related injuries has previously been extensively studied and reported on³⁻⁷. These reports have mainly concentrated on causes for and findings at ex-lap, and postoperative mortality (table 1). Few studies have focused on the differences in injury mechanism, complexity of injuries and outcome between civilians and combatants, especially in urban conflicts where IED's, human shields and suicide bombers are used².

Table 1. Findings at ex-lap and postoperative mortality in different conflicts

Conflict	Nb. of Ex-laps	Negative explorations	Small intestinal injuries	Colon injuries incl. rectum	Other injuries	Postoperative mortality
Chad,1980³	210	4,8%	33,0%	21,1%	32,7%	22,5%
Lebanon 1975-85⁴	1314	9,7%	24,7%	21,2%	55,0%	9,5%
Former Yugoslavia 1991-95⁵	93	4,3%	30,0%	28,4%	41,5%	10,8%
Gaza 2000-03⁶	230	6,5%	26,7%	17,9%	55,3%	7,4%
Mosul, Iraq, 2006⁷	153	15%	23,7%	18,7%	57,6%	33,3%

Justification

There is a need for better understanding of demographics and outcome of ex-lap following abdominal injuries sustained in urban conflicts where IEDs, human shields and suicide bombers are used. The use of these indiscriminate weapons could affect civilians to a greater extent than combatants⁸. We therefore hypothesize that the use of indiscriminate weapons in an urban setting causes more extensive abdominal injuries to the civilian population than to combatants. The knowledge gained from this study could be crucial when planning surgical staffing and facility needs in similar contexts.

Potential Risks and Benefits

Since this is an observational retrospective cohort study without any interventional methods it poses little to no harm for the participants. A potential benefit for future patients would be an increase in understanding among health care providers regarding what kind of abdominal injuries indiscriminate weapons cause. Furthermore, a better understanding of what impact the use of indiscriminate weapons has on the civilian population.

Aim of Study

To assess whether civilians have more complex abdominal injuries than combatants in an urban battle characterized by the use of indiscriminate weapons.

Primary Measure

Differences in injury mechanism, organs injured, surgical treatment given, postoperative complications and outcome between civilians *and* combatants.

Secondary Measures

Comparison of surgical treatment given, postoperative complications and outcome between patients with prior surgical treatment of their injury *and* patients without prior surgical treatment.

Differences in surgical treatment given, postoperative complications and outcome between patients who receive surgical treatment less than 24 hours from injury *and* patients who receive surgical treatment more than 24 hours from injury will be analysed.

See chapter Data, *patient files*, for detailed primary and secondary measurements.

Investigation Plan

Study Design

A cohort study with retrospective longitudinal data collection using routinely collected clinical data.

Study Period

Consecutive patients presenting at EH between October 17, 2016 and July 16, 2017 that meet eligibility criteria will be included. Patient history information preceding hospital admission will be included.

Study Location

Emergency Hospital, Erbil, Kurdistan Region, Iraq.

Study Duration for Participants

Participants will be followed from admission until discharged from EH.

Study Population

Recruitment Methods

Patients will be included from the surgical ledger at the Surgical Department of EH.

Inclusion Criteria

- All patients treated with ex-lap due to conflict-related penetrating injury presenting at EH between October 17, 2016 and July 31, 2017 will be included.

Exclusion Criteria

- Patients who received treatment several times during the study period will only be counted as one patient.

Information for Patients and Consent

Since this study is based on data from routine care participants will not be informed, nor will consent be asked of participation, as this could introduce bias and confounding factors. There are moreover no risks or potential gains involved for participants. No incentives or inducements will be provided to any participant or staff involved.

Data

Data Sources

Data was routinely prospectively collected on paper based patient forms in the clinical setting at EH. A *patient database* with consecutive patients treated between October 17, 2016 and July 31, 2017 was created. It is expected that the database will contain a total of 1,800 patients to produce approximately 160 evaluable subjects. Paper based *patient files* will be queried for demographic information, combatant or civilian status, admission dates, discharge dates, whether the injury was conflict-related or not, geographical site for injury, cause and mechanism of injury, prehospital data, medical history, vital signs at hospital admission, anatomical data and details regarding extent of abdominal injury, number and type of surgeries, details on surgery, need for ICU care, in hospital complications, re-admission including cause of re-admission, outcome including death and cause of death. Paper based data will be entered into a computer database using Epidata entry software (The Epidata Association, Odense, Denmark).

Patient Files

- Time of admission (specified)
- Age in years (specified)
- Sex (Male/Female/Unknown)
- Ethnicity (Arabic/Kurdish/Other/Unknown)
- Civilian/Combatant (Iraqi/Peshmerga/ISg/Unknown/Other)
- Time of injury (specified)
- Geographical location where injury occurred (specified)
- War-related injury (Yes/No/Unknown)
- Cause of injury (Bullet/Shell/Mie/IED/Unknown/Other)
- Mechanism of injury (Gunshot/Stab/Blast/Crush/Fragment/Burn/Traffic accident/Unknown/Other)
- Care prior to admission to EH (First Aid/Medical/Surgery/None given/Unknown)
- Provider of care prior to EH (MSF/Aspen/ICRC/Samaritan Purse/DoH/None)
- Mode of transport to EH (Military/Private car/Motorcycle/Ambulance/Unknown)
- Medical history (Healthy/Prior surgery/ Prior medical/Unknown)
- Body temperature (specified in Celsius)
- Heart rate (specified in beats/min)
- Blood pressure (specified in systole/diastole mmHg)
- Pregnant (Yes/No/Unknown)
- Pregnancy status based on (Lab/Question/Status/Unknown)
- Site and extent of abdominal wound (specified)
- Other injuries (Yes/No/Unknown, specified)
- Preoperative haemoglobin (specified in g/dL)
- Preoperative transfusions (Yes/No/Unknown, specified)
- Use of preoperative radiology (Yes/No/Unknown, specified)
- Time and date of procedure (specified)
- Duration of procedure (specified in hours and minute)

- Antibiotics prophylaxis (Yes/No/Unknown, specified)
- Procedure done (appendix 1 for definition of findings)
- Perioperative complication (Yes/No/Unknown, specified)
- Postoperative antibiotic prophylaxis (Yes/No/Unknown, specified)
- Postoperative infection (Yes/No/Unknown, appendix 3 for definition)
- Other postoperative complication (Yes/No/Unknown, appendix 2 for definition)
- Need of postoperative intensive care (Yes/No/Unknown, specified)
- Postoperative transfusions (Yes/No/Unknown, specified)
- Use of postoperative radiology (Yes/No/Unknown, specified)
- Further surgery done (Yes/No/Unknown, specified)
- Discharge (Yes/No/Unknown, specified)
- Follow-up scheduled (Yes/No/Unknown, specified)
- Re-admission (Yes/No/Unknown, specified)
- Deceased during hospital stay (Yes/No/Unknown, specified)
- Remarks

Statistical Analyses

Sample Size

Due to the nature of the study, the sample size will be a convenience sample of the available cases during the study period. It is expected that approximately 160 subjects will be enrolled.

Statistical Methods

Analysis will be done by as treated. A 5% significance level will be used. The difference in dichotomous, such as postoperative complication (primary outcome), and categorical outcomes with more than two categories will be tested using chi-square or Fisher test. For differences in continuous variables t-test will be used. In order to adjust our analysis for possible confounders and effect modifiers we will then use linear, logistic, ordinal or multinomial regression models, according to the nature of the outcome (continuous, binary, ordinal or nominal) with injury mechanism as the dependent variable and civilian/combatant as the main explanatory variable. Important demographic and injury specific parameters such as geographical location, date, age, sex, and injured organs, will then be included in the model as potential confounders.

Safety and Monitoring

Participant Confidentiality

The use of identification numbers will ensure anonymity in the data analysis. The participant's age, gender and demographic characteristics will be used as identifying features for analysis. The research team will ensure the ethical principles of beneficence, non-maleficence, justice and respect of patients are adhered to throughout the study.

Data Collection and Management

All data will remain anonymous throughout the data entry and analysis process. Nominal data will not be distributed outside the study location, or appear in any report or publication. Participant names will only be known by the research team. Identification codes will be safeguarded at EH facilities for the duration of the study.

Ethical Considerations

Ethics

The study will be conducted according to ethical principles stated in the Declaration of Helsinki⁹.

Ethical Review Board Approval

An approval from the Ethics Review Committee of the Directorate of Health, Department of Health, Erbil, Kurdistan Regional Governate will be obtained before initiating the study.

Conflict of Interest

This is an investigator-initiated study. No company has had any influence over study design. There are no known conflicts of interest with other parties.

Dissemination

Printed and electronic versions of the final report will be provided to all partners involved in this research. Main findings will be presented orally to hospital staff at EH. The research methodology and results will be presented at scientific conferences and published in peer-reviewed journals.

References

1. Cockburn P. The rise of Islamic state : ISIS and the new Sunni revolution. London ; New York: Verso 2015.
2. Affairs UNOfD. Improvised Explosive Devices (IEDs) [WWW]. New York, USA2016 [Available from: <https://www.un.org/disarmament/convarms/ieds2/> accessed 28 May 2017.
7. Borhan MS A-NH. Analysis of Abdominal Missile Injuries: Prospective Study in Mosul. , 2008.

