Appendix 4: Case Report Form

Exploratory laparotomy following penetrating abdominal injuries: a cohort study from a referral hospital in Erbil, Kurdistan region in Iraq

Case Report Form

1 November 2017

FINAL version

Case Report Form (CRF), version 171101, protocol: _____

Patient Data

Patient no

1. Time of admission

 / /

day month year

 :

hours minutes

Unknown

2. Age

 in years

Unknown

3. Sex

Male

Female

Unknown

4. Ethnicity

Arabic

Kurdish

Other

Unknown

If other, specify

5. Civilian/Combatant

Civilian

Combatant

Unknown

If combatant

Iraqi

Peshmerga

IS

Unknown

Other

If other, specify

Investigators signature _____

day month year

Validated by and date: _____

Case Report Form (CRF), version 171101, protocol: _____

Injury Data

Patient no

[figure not shown]
6. Time of injury

hours minutes

day month year

Unknown

7. Geographical location where injury occurred

Unknown

Other

If other, specify location where injury occurred

Investigators signature

day month year

Validated by and date: _____

Case Report Form (CRF), version 171101, protocol: _____

Injury Data continued

Patient no

8. War-related injury

Yes

No

Unknown

9. Cause of injury

(If several causes number in same order as question 20 and 21)

Bullet

Shell

Mine

IED

Unknown

Other

If other, specify

10. Mechanism of injury

(If several number in same order as question 20 and 21)

Gunshot

Stab

Blast

Crush

Fragment

Unknown

Burn

Other

Traffic accident

If other, specify

Investigators signature _____

_____/_____/_____
day month year

Validated by and date: _____

Case Report Form (CRF), version 171101, protocol: _____

Prehospital Care Data

Patient no

11. Care prior to admission to EH

(If several number in chronological order)

First aid

Medical

None given

Unknown

Surgery

If surgery, specify procedure done

day month year

of procedure

12. Provider of care prior to EH

(If several number in chronological order)

MSF

Aspen

ICRC

Unknown

Samaritan Purse

None

Department of Health

Other, specify

Investigators signature

day month year

Validated by and date: _____

Case Report Form (CRF), version 171101, protocol: _____

Prehospital Care Data cont.

Patient no

13. Mode of transport to EH

(If several number in chronological order)

Military

Private car

Motorcycle

Ambulance

Unknown

Other, specify

14. Medical history

Healthy

Unknown

Prior surgery

Prior medical

If prior surgery specify procedure(s)

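### The civilian and combatant definitions overlap and can conflict with recorded status, and the plan does not say which source defines the main exposure

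*Combined protocol and SAP*

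**What the plan says.** **The rule.** The List of Definitions gives civilians as "Children <16 years, all women and men" aged 50 or over, and combatants as "Men 16-50 or combatants by own admission".

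**The record.** Under Data Sources, "Data was routinely prospectively collected on paper based patient forms in the clinical setting at EH", and the patient files "will be queried for demographic information, combatant or civilian status, admission dates, discharge dates". The Patient Files list carries the variable as "Civilian/Combatant (Iraqi/Peshmerga/ISg/Unknown/Other". In Appendix 4, "5. Civilian/Combatant" offers Civilian, Combatant or Unknown, with affiliation asked if combatant. Items 31 and 32 of the same form point to the appendices that define them. Item 5 points to no definition.

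**The analysis.** Under Statistical Methods, dichotomous and categorical outcomes are first compared without adjustment (chi-square or Fisher). Then: "In order to adjust our analysis for possible confounders and effect modifiers we will then use" regression models "with injury mechanism as the dependent variable and civilian/combatant as the main explanatory variable". Age and sex are among the listed confounders. The form of the age term is not stated, the effect modifiers are not named, and nothing is said about patients of Unknown status.

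**The concern.** Civilian versus combatant is the contrast in the aim, the primary objective and the main model. Definitions that are not mutually exclusive, next to a recorded variable that need not agree with them, let two analysts put the same patient in different groups. The choice could then be made after the data are seen.

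The second issue is conditional. If the rule supplies the exposure, the planned adjustment puts age and sex into a model whose main explanatory variable is built from age and sex. The coefficient then depends on how age is modelled. In addition, every true civilian man aged 16-49 counts as a combatant, which dilutes the contrast.

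**Working it through.** The plan has no figure of its own to reproduce here. Its approximately 160 patients are a convenience sample, with no group split, effect size or power.

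**1. Boundary cases, from the two definitions as written**

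| Patient | Meets civilian definition | Meets combatant definition |
|---|---|---|
| Man aged 50 | yes | yes |
| Woman aged 30, self-admitted combatant | yes | yes |
| Boy aged 15, self-admitted combatant | yes | yes |
| Man aged 60, self-admitted combatant | yes | yes |
| Man aged 30, no admission | no | yes |

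Self-admission can only add combatants. Under the rule, then, no man aged 16-49 can be a civilian, and any such man recorded as Civilian in item 5 is in conflict with it.

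**2. What adjustment does under the rule, leaving self-admission aside**

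Take main effects for status (c), sex (m) and three age bands, with 16-49 as reference and k the effect of an outer band. The linear predictors are:

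- men in an outer band: a + m + k + c
- men 16-49: a + m
- women in an outer band: a + k + c
- women 16-49: a + c

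(men outer − men 16-49) − (women outer − women 16-49) = (k + c) − k = c.

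So c can be estimated (design rank 5 of 5), but only as a sex-by-age contrast that needs women outside 16-49. Assuming 80% male and 35%, 22% or 15% of patients outside 16-49, that is 160 × 0.2 × 0.35, 0.22 or 0.15 = 11.2, 7.0 or 4.8 women. With linear or quadratic age, the assumed curve does the separating.

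**3. Illustration of size**

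From the plan: n = 160 and the 5% level. Assumed: 80% male; age mixes (<16 / 16-49 / ≥50) of 20/65/15, 15/78/7 and 10/85/5%; ages uniform within 2-15, 16-49 and 50-74; a generic binary outcome with 30% baseline risk. The fit is logistic with a Wald test, and non-converged fits count as not significant. False findings have no civilian effect and an age odds ratio of 2 in both outer bands. Power is for a civilian odds ratio of 2.5 with no age effect. Results follow the order of the mixes.

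| Model, rule as exposure | False civilian finding | Power |
|---|---|---|
| Unadjusted | 33.8 / 23.2 / 17.1% | 80.3 / 77.5 / 74.3% |
| Sex + linear age | 42.5 / 33.2 / 27.8% | 66.0 / 52.8 / 41.2% |
| Sex + quadratic age | 11.7 / 10.2 / 9.5% | 34.1 / 26.6 / 21.2% |
| Sex + age bands | 2.9 / 3.2 / 1.5% | 17.8 / 13.6 / 8.2% |

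Up to 20.1% of the band fits in the false-finding runs, and 17.8% in the power runs, did not converge.

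Other age effects, with linear age:

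- U-shaped odds ratio of 1.5: 12-18% false findings.
- Odds ratio of 2 in only one outer band: 8-16%.
- No age effect, or a steady trend (0.5 below 16 and 2 from 50): 3-6%.

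A separate run with a skewed continuous age distribution, 25% baseline risk and a smooth U-shape gave 31% (linear), 5.0% (quadratic) and 3.6% (bands).

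**4. The same outcome model with independently recorded status**

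Assume 20-40% of men aged 16-49 are recorded as civilians. With the U-shaped odds ratio of 2, false findings are 5-9% with quadratic age and 4-5% with bands. Power is 54-65% and 44-61%. Linear age still gives 8-29% false findings.

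**5. Dilution**

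If a fraction f of rule-combatants are really civilians with the same risk as other civilians, the unadjusted difference shrinks by the factor (1 − f). Let q be the combatant share under the rule; the first mix gives 0.8 × 0.65 = 0.52. The sample-size multiple is

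[q(1−f)(1−q(1−f))] / [q(1−q)(1−f)²] = (1 − q(1−f)) / ((1−q)(1−f)).

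- f = 0.2: 0.584 / 0.384 = 1.52
- f = 0.3: 0.636 / 0.336 = 1.89
- f = 0.4: 0.688 / 0.288 = 2.39

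**The case against.** The strongest reply is that there is only one source. The List of Definitions may be the instruction for filling in item 5. The CRF is dated 1 November 2017, after the study period, so it is a retrospective abstraction form. Affiliation is asked only of combatants, and Unknown is needed anyway because age and sex can be missing. This reading is tenable, but the documents do not state it. If it is right, the overlaps remain and the conditional problem in steps 2, 3 and 5 becomes the actual one.

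The contradiction may also be called small. The self-admission clause adds something only if it overrides age and sex, so precedence can be inferred. For men aged exactly 50, the assumptions of step 3 give 160 × 0.8 × 0.05 to 0.15 / 25 = 0.26 to 0.77 expected patients. That stands: the age-50 overlap alone is a wording correction. The larger exposure is men aged 16-49, whom the rule can never call civilian.

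The simulated rates can be challenged too. They need an age effect that the chosen age term misses, and in step 3 that effect shares the rule's cut-points. The model's stated dependent variable is injury mechanism, which has several categories, so the figures do not transfer directly. Finally, if the purpose is to describe who needs which surgery, an unadjusted group difference that arises through age is still a real difference. Calling it false applies only when it is read as an effect of being a civilian. These points stand and limit what may be claimed.

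**Conclusion.** The definitions of the main exposure are wrong as written. They are not mutually exclusive, they classify every man aged 16-49 as a combatant, and no section says whether they or recorded status govern. This follows from the text and needs no assumptions.

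The modelling consequence holds only if the rule supplies the exposure. The adjusted civilian effect then depends on an unstated age term, and true civilian men aged 16-49 dilute the contrast. The direction is clear but the size is not known: the illustration runs from 3-6% false findings (no age effect or a steady trend, linear age) to 28-43% (U-shaped odds ratio of 2, linear age).

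Three stronger readings are tempting but not supported:

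- **That the adjusted effect cannot be estimated.** Rank fails only with added terms such as age band by sex (6 of 7) or civilian by sex (5 of 6). The plan mentions effect modifiers but specifies none of these terms.
- **That the study will report a spurious civilian effect.** The documents give no age effect from which to conclude this.
- **That item 5 is an independent record and should simply replace the rule.** No section says how it was filled in.

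**What to change.** 1. Make the definitions mutually exclusive: put age 50 on one side only, and state that self-admission overrides age and sex.
2. State how item 5 was filled in, and cross-tabulate it against the rule before any outcome analysis.
3. If item 5 was recorded independently of the rule, make it the primary exposure. Adjust for sex and a prespecified flexible age term, not linear age alone. Keep Unknown status out of the primary comparison, and report the rule as a sensitivity analysis.
4. If item 5 was derived from the rule, describe the contrast as one between demographic groups. Do not interpret an age- and sex-adjusted coefficient as an effect of being a civilian. The unadjusted result also carries any age effect and needs the same caution.

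The cost is revised wording and one cross-tabulation, with no new data for these steps. In case 4, obtaining an independent status would mean going back to the files. Recorded status may be misreported or incomplete, and patients of Unknown status drop out of the primary comparison. The documents do not say how many there are.

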Appendix 3: Surgical Site Infection defined by WHO¹³

- Superficial incisional, affecting the skin and subcutaneous tissue. These infections may be indicated by localized signs such as redness, pain, heat or swelling at the site of the incision or by the drainage of pus.
- Deep incisional, affecting the fascial and muscle layers. These infections may be indicated by the presence of pus or an abscess, fever with tenderness of the wound, or a separation of the edges of the incision exposing the deeper tissues.
- Organ or space infection, which involves any part of the anatomy other than the incision that is opened or manipulated during the surgical procedure, for example joint or peritoneum. These infections may be indicated by the drainage of pus or the formation of an abscess detected by histopathological or radiological examination or during re-operation. Organ infection is not included within the scope of this guideline.

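### Two definitions of surgical site infection are left unreconciled, and one of them counts any reopening of the surgical site as infection

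*Combined protocol and SAP*

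**What the plan says.** The SSI entry in the List of Definitions reads "Surgical Site Infection is present when one of the following criteria are met". It then lists four alternatives: purulent discharge, a positive culture, "Surgical site requires reopening", and the attending physician's judgement. The reopening criterion carries no reason, sign or exclusion. The entry uses Appendix 3 only to grade: "Severity according WHO guidelines (appendix 3".

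The Patient Files list gives Appendix 3 a different role: "Postoperative infection (Yes/No/Unknown, appendix 3 for definition". CRF item 31 refers to the same appendix for its definition. Appendix 3 describes superficial, deep and organ/space infection by their signs. Re-operation appears only as one setting in which pus or an abscess may be found. For organ/space infection it says "These infections may be indicated by the drainage of pus or the formation of an abscess detected by histopathological or radiological examination", and then adds re-operation as a third way of detecting them.

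Re-operation has its own variable, "Further surgery done (Yes/No/Unknown, specified", which is CRF item 36. The Statistical Methods section labels postoperative complication, not SSI, as the primary outcome. One of the two secondary comparisons sets "patients with prior surgical treatment of their injury" against patients without prior surgery.

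**The concern.** One abstractor working from the List of Definitions and another working from item 31 and Appendix 3 could code the same re-laparotomy differently. The first would record SSI for any reopening. The second would look for signs of infection.

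If the literal rule is used, the SSI rate mixes infection with surgical re-intervention. That matters for group comparisons if non-infective reopening is more frequent in one group.

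The prior-surgery comparison is the most exposed. Every participant has a laparotomy at EH, and the Background says that EH served mainly as a referral hospital after late December 2016. If the earlier operation elsewhere was a laparotomy, the operation that qualifies the patient for the study may itself reopen that site. Read literally, the criterion could then be met by the entry procedure, and only in the prior-surgery group.

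In the civilian/combatant comparison, the study's own hypothesis of more extensive injury in civilians makes unequal reopening plausible, but no more than that.

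**Working it through.** **The texts side by side**

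| Event | List of Definitions, read literally | Appendix 3, as used by item 31 |
|---|---|---|
| Re-laparotomy for bleeding, no signs of infection | SSI | Not indicated as SSI |
| Planned second look, no signs of infection | SSI | Not indicated as SSI |
| EH operation reopening an outside laparotomy, no signs of infection | Possibly SSI | Not indicated as SSI |
| Reopening that finds pus or an abscess | SSI | SSI |

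**Illustration of size**

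The plan states no SSI rate, reopening rate or group split, so it has no figure to reproduce. From the documents come the expected total of about 160 and the 5% significance level (two-sided assumed). The following are assumptions: true SSI s = 15% in both groups; non-infective reopening at rate r, independent of SSI; groups of 53 and 107.

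Recorded SSI = 1 − (1 − s)(1 − r). For r = 10% this is 1 − 0.85 × 0.90 = 23.5%. For 5%, 20% and 30% it is 19.25%, 32.0% and 40.5%.

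The rejection probability is the sum of the two binomial probabilities over all tables that the uncorrected chi-square test calls significant:

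| Reopening, group of 53 v 107 | Recorded SSI | Difference (points) | Rejection probability |
|---|---|---|---|
| 10% v 10% | 23.5% v 23.5% | 0 | 5% |
| 5% v 10% | 19.25% v 23.5% | 4.25 | 9% |
| 10% v 20% | 23.5% v 32.0% | 8.5 | 19% |
| 10% v 30% | 23.5% v 40.5% | 17.0 | 57% |

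If the smaller group has the higher rate, the last three become about 10%, 22% and 61%. With Fisher's test, which the plan also allows, the last two rows become about 17% and 53%.

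**Equal reopening rates**

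Equal rates create no false difference but weaken a real one. Take an assumed true SSI of 15% v 35% and reopening of 10% in both groups. Recorded SSI is 0.15 + 0.85 × 0.10 = 23.5% and 0.35 + 0.65 × 0.10 = 41.5%. The odds ratio falls from 3.05 to 2.31. With 80 per group, power falls from about 84% to 68% (normal approximation).

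**The outcome labelled primary**

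Under Appendix 2, an intervention under general anaesthesia for a complication is already Clavien-Dindo grade III-b. Relabelling such a re-operation as SSI leaves a yes/no complication variable unchanged. Only an event that is not otherwise a complication can change it, such as a planned second look or the qualifying EH reopening.

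Suppose 50% truly have a complication, and a planned second look occurs in 5% v 10% of the rest. The recorded rates are 0.50 + 0.50 × 0.05 = 52.5% and 0.50 + 0.50 × 0.10 = 55.0%. With groups of 53 and 107 the rejection probability is about 6%, close to nominal.

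**The case against.** The strongest reply is that the collection form already prevents the problem. Item 31 records infection by layer, as sepsis or as unspecified infection, each with a date of diagnosis. It has no box for reopening and stands under postoperative data. Surgery before EH is recorded separately in item 11 with procedure and date, and it need not have been a laparotomy. Later re-operation goes to item 36. An abstractor who follows the form alone would not code a second look, or the EH operation itself, as infection.

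This stands as far as it goes. It rules out a reading that the literal rule may tempt, namely that every reopening will be recorded as infection and that the main comparison is therefore biased. The documents do not support that. Nor do they support saying that prior-surgery patients become SSI cases automatically. That would need the List of Definitions to be applied literally, the form's structure to be set aside and the earlier operation to have been a laparotomy.

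The reply does not remove the conflict, because no section subordinates one definition to the other.

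Three further limits apply. Appendix 3 says what may indicate infection and does not strictly require those signs. Its closing sentence, "Organ infection is not included within the scope of this guideline", concerns the scope of the guideline and is not a study exclusion, since item 31 includes the abdominal cavity. Anastomotic leak is a poor example of non-infective reopening, because organ/space infection in Appendix 3 covers the peritoneum.

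**Conclusion.** Wrong as written, minor. The firm finding is textual: there are two SSI definitions, neither is said to govern, and one makes reopening for any reason sufficient.

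The consequences are conditional. The SSI rate is inflated only if the literal rule is used. A false group difference also needs unequal non-infective reopening, which is most plausible in the prior-surgery comparison. The figures of 9%, 19% and 57% concern SSI alone and rest entirely on assumed rates and an assumed split. The largest needs a threefold difference in reopening.

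A reader might infer that the outcome labelled primary is materially biased. It is largely protected, with the planned second look and the qualifying EH reopening as the exceptions. SSI is not named as a separate endpoint in the objectives or the Statistical Methods section.

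**What to change.** - State that one SSI definition governs CRF item 31.
- Reword the third criterion as: *surgical site reopened because of suspected or confirmed infection*.
- State that the qualifying EH laparotomy, and re-operations without infection (for example for bleeding or as a planned second look), are recorded under operative data or item 36 and are not SSI by themselves.
- Use Appendix 3 only to grade depth, including the abdominal cavity as item 31 already does.
- Optionally, add a sensitivity analysis that drops the third criterion. Abstractors would then need to note when it is the only criterion met, because item 31 does not record which criterion applied.

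The cost is a short wording change and no new data source, since the paper files are already being read. Abstractors must find the reason for each reopening, which item 36 does not ask for separately. Some reasons will be unknown, and the plan should say how those are coded. If abstraction has begun, files with a re-operation or a prior laparotomy need a second look at item 31.
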